“Serious” means an adverse experience that is fatal or life-threatening, is permanently disabling, requires or prolongs inpatient hospitalization, or is a congenital anomaly, cancer or overdose.

At enrollment, the subjects will be informed of known perampanel-adverse side effects such as dizziness, sleepiness, tiredness, irritability, falls, nausea, problems with muscle coordination, problems walking normally, vertigo, weight gain, headache, vomiting, abdominal pain, and anxiety. The potential serious adverse side effects of perampanel will be highlighted, and subjects advised to immediately contact the investigators if any serious adverse effects occur. Subjects who have homicidal or aggressive behavior will be evaluated by the Investigator. The drug will be discontinued, and if the Investigator determines that the subject or others are at risk, appropriate measures to ensure the safety of the subject and others.

Serious adverse side effects for perampanel in the controlled Phase 3 epilepsy clinical trials included hostility- and aggression- related adverse reactions occurred in 12% and 20% of patients randomized to receive perampanel at doses of 8 mg and 12 mg/day, respectively, compared to 6% of patients in the placebo group (FDA label, 2016). Three patients (0.1%) out of 4,368 perampanel-treated patients exhibited homicidal ideation or threat in controlled and open-label studies, including non-epilepsy studies. These effects were dose-related (less at 4mg) and generally appeared within the first 6 weeks of treatment. A review of the phase I, II, and III studies concluded that the incidence of hostility/anger was not different from placebo in doses \leq 8 mg (Ettinger et al, 2015).

U.S. Prescribing Information for all AEDs includes the following language: “AEDs increase the risk of suicidal thoughts or behavior in patients taking these drugs for any indication.”

The investigators have conducted multiple studies with healthy volunteers on the cognitive effects of antiseizure medications with an excellent safety record (see 15 References

from Prior Healthy Volunteer ASM Studies by [name]). Almost all side effects are mild or moderate and reversable. No long-term sequelae have ever occurred.

If any medically serious adverse event occurs (SAE), the study medication may be discontinued, and the subject treated at the discretion of the physician investigator.

ANY MEDICALLY SERIOUS ADVERSE EVENT REQUIRES IMMEDIATE NOTIFICATION OF THE FDA BY THE INVESTIGATOR.

Any serious adverse event that occurs up to two weeks following study participation must also be reported.

Serious adverse events must be reported to the lead site principal investigator, [name], within 24 hours of the site becoming award of the SAE.

Serious adverse events must be reported to sites' institutional review boards (IRB) according to their IRB's regulations.

Specific procedures for Double-Blind Studies

Site personnel not involved in direct care of study subjects will generate a randomization code. In an acute medical emergency, the randomization code may be broken if this is considered essential for subject management. For this purpose, the sealed randomization code will be provided to the investigator by the site pharmacy. If the code is broken, a record of the date, time and reason must be put into writing and sent to Eisai. This letter will become part of the permanent study record.

All adverse events should be recorded on the appropriate Case Report Forms (CRF's) including date of onset and cessation, intensity and relationship to study drug. The action taken and clinical outcome of the adverse event will also be recorded.

The investigator will report all serious AE's to the FDA and to Eisai without delay.

D. Medication Compliance Assessment

Compliance is to be judged by questioning the patient at the clinic visit and by the non-blinded observer's inspection of medication returned and recording missed doses on the appropriate CRF. Repeated noncompliance, or the missing of all scheduled doses of medication for three (3) consecutive days (72-hour period) would be cause for removing the subject from the study. Subjects should take all doses for 3 days before visits when cognitive function testing occurs.

E. Subject Discontinuation Criteria

1. Although they may withdraw without prejudice at any time, every effort should be made to have subjects complete the study within the bounds of safety and provisions of informed consent.
2. The investigator may discontinue the participation of any subject in this study if:
 - a. Any clinically significant adverse experiences are observed.
 - b. The subject is grossly noncompliant.
 - c. The subject's health would be jeopardized by continued participation.
 - d. Consent is withdrawn. Subjects will be encouraged to complete the study, although they may withdraw at any time without prejudice.
4. Subject replacement.

Subjects who are dropped from the study prior to completion of all cognitive testing will not be replaced.

Subjects who are withdrawn prior to completion of at least one set of cognitive testing on treatment drug (i.e., prior to visit 5/study week 3) may be replaced.

5. Follow-up of discontinued patients

Subjects who receive study drug and are discontinued from the study will have all safety assessments completed, including a complete physical examination and laboratory evaluation including chemistry, hematology with differential, urinalysis and urine pregnancy test as required at study termination. This testing should be done as soon as possible. Medical follow-up of any severe adverse events or clinically significant abnormal laboratory values will continue until the abnormality resolves, and adequate medical explanation is apparent. Such data will be provided to Eisai.

X. STATISTICAL EVALUATION

A. Sample Size

We assume that the 4 groups (3 PER treatments and a placebo group) are equally spaced (in terms of z-score) at the time point of maximum drug effects (end week 1 for 4mg group and end week 3 for titration to 2mg x2wks then 4mg group), with a maximum difference of 0.24 (which is the difference between the placebo group and treatment at max effect). We then assume that over the 4 visits after max drug effect the z-scores get closer together until

they are equal at the treatment week 6th. The calculation indicates that at least 18 subjects are needed in each group to have 80% power. Since there are 4 groups, the total sample at least finishing assessment at end of week 6 (event 8) would be $19 \times 4 = 76$. Enrollment will include 20% (n=15) more to account for dropouts prior to assessment at end of visit 2 (baseline), and ~15% (n=12) more for dropouts before end of event 8 (treatment week 6). Thus, the total enrollment sample will be 103 subjects.

In summary, the 4 total groups (3 PER treatment, 1 placebo) would need at least 19 subjects per group (76 total), and total enrollment would be rounded to 105 to account for dropouts.

B. Methodology for statistical analysis

The parameters of interest are listed in Section VII. Descriptive statistics will be used to provide an overview of the primary, secondary, and other variable results. For categorical parameters, the number and percentage of subjects in each category will be presented. The denominator for percentages will be based on the number of subjects appropriate for the purpose of analysis. For continuous parameters, descriptive statistics will include number of subjects, mean, standard deviation (SD), median, minimum, and maximum. Unless otherwise specified, baseline neuropsychological data will be based on the Visit 2 assessments.

Study question 1: What are the behavioral, cognitive or other side effects of perampanel at different titration rates in healthy volunteers?

The primary outcome variable will be the overall neuropsychological composite z-scores for the objective and subjective measures combined.

Study question 2: What is the time course of habituation to objective vs. subjective neuropsychological (e.g., cognitive and behavioral) side effects of perampanel?

The primary outcome variable will be the neuropsychological composite z-scores for the objective and subjective measures, which will be analyzed separately.

The objective measure z-score will be calculated by averaging overall computerized and noncomputerized cognitive z scores, which are calculated by averaging individual z-scores of selected performance measures from the computerized cognitive test battery (i.e., average of z-scores for the domain scores for executive function and for processing speed) and from the noncomputerized cognitive test battery (i.e., average of individual z-scores for MCG immediate, MCG delayed, SDMT, and Stroop-average score). The subjective measure z-score will be calculated by averaging the individual z-scores for AEP, POMS, and QOLIE-cognitive questions (average of 3 scores from QOLIE). These z-scores will be assessed by a 4 (titration rate) \times 6 (time: weeks 1-6) ANCOVA controlling for scores at Baseline (visit 2) using an intent-to-treat analysis for those receiving neuropsychological testing at least at the end of week one. Imputations will be employed for dropout after week one.

We will control for differences across groups in age, gender, and personal/family history of psychiatric disorders.

This method with a similar overall score has been employed in prior investigations. This approach avoids potential Type I errors from multiple statistical comparisons and Type II errors resulting from reduced statistical sensitivity as a result of correcting for multiple comparisons. Analyses of individual components of the computer and neuropsychological assessment are secondary endpoints meant to evaluate sensitivity of the primary endpoint and examine the pattern of neuropsychological effects. All other endpoints are supportive and are safety assessments. Hence no adjustments for multiplicity are planned. P-values for these safety variables are not meant to show superiority and thus testing each of these variables at the $p=0.05$ level without multiplicity adjustment is a more conservative approach, which is appropriate for safety assessments and for secondary analyses of the pattern of impairments. The importance of the results should be evaluated in terms of actual differences and the risk/benefits offered by the drug to the patients.

The secondary outcome variables will be:

1. Compare titration rates for changes from Baseline (visit 2) to the end of titration (study week 3) and end of maintenance (study week 6) using Z-scores from full neuropsychological battery. The outcome variable for this analysis will be an overall neuropsychological composite Z-score, calculated by averaging individual z-scores of the selected performance measures from the computerized cognitive test battery (i.e., z-scores for the domain scores for executive function and processing speed), the average for individual Z-scores for AEP, POMS, QOLIE-cognitive questions (average of 3 scores), and the noncomputerized cognitive scores (i.e., average of z-scores for MCG immediate, MCG delayed, SDMT, Stroop-average score).
2. Compare titration rates for TEAEs and dropouts due to TEAEs across visits 3-8 (i.e., weeks 1-6).
3. Separate comparisons of titration rates for behavioral overall scores and cognitive overall scores.
4. Comparisons of titration rates and habituation over time for individual measures.

Summary statistics will be calculated by treatment for each evaluation of antiepileptic blood levels (ABLs). Additional analyses of data will be performed which take the ABLs into account. Linear correlations of plasma concentrations and the overall composite and individual score variables will be plotted with a fitted regression line superimposed for each condition.

The incidences of all adverse events reported during the trial will be tabulated by treatment and study period. The other safety variables, which include changes in hematology, clinical chemistry, and urinalysis parameters, and vital signs will be analyzed descriptively. The actual measurement and its change from baseline will be presented by visit and period of collection. In addition, shift tables may be used to evaluate the number and percentage of subjects having a different post-baseline status when compared with their baseline status.

C. Interim Analysis

No interim analyses are planned.

D. Definition of Evaluable Subjects

Any subject who ingested one or more doses of blinded study medication and provided follow-up information will be evaluable for the analysis of the safety data. The primary analysis will include subjects who complete all visits or at least one set of cognitive/behavioral testing on treatment drug and who did not have any important deviations, which may have an impact on cognitive function. Subjects who prematurely discontinue the study will be evaluated based on the data collected at each visit attended. Any subject who is evaluable for the safety analysis who also has baseline and end of drug period cognitive/behavioral data available will be evaluable for the intent-to-treat analysis of the parameters of interest. Any subject evaluable for the intent-to-treat analysis will be evaluable for the per-protocol analysis of the parameters of interest provided that the subject was compliant with the protocol with regard to the study medication regimen, use of concomitant medications, sleep requirements prior to cognitive testing, alcohol consumption, caffeine consumption, and use of OTC medications prior to cognitive testing. All data will be used to their maximum possible extent, but without any imputations for missing data for any parameter.

XI. REFERENCES:

1. Background References.

French, J. A., Krauss, G. L., Steinhoff, B. J., Squillacote, D., Yang, H., Kumar, D., & Laurenza, A. Evaluation of adjunctive perampanel in patients with refractory partial-onset seizures: results of randomized global phase III study 305. *Epilepsia* 2013;54(1), 117-125.

Krauss, G. L., Bar, M., Biton, V., Klapper, J. A., Rektor, I., Vaiciene-Magistris, N., ... & Kumar, D. Tolerability and safety of perampanel: two randomized dose-escalation studies. *Acta Neurol Scand* 2012a;125(1):8-15.

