B. Inclusion Criteria

1. Healthy adults between the ages of 18 and 55 years
2. Male or female (using approved birth control methods)
3. Informed consent obtained

C. Exclusion Criteria

1. Presence of clinically significant cardiovascular, endocrine, hematopoietic, hepatic, neurologic, psychiatric, or renal disease.
2. Presence or history of drug or alcohol abuse or positive urine drug test at screening.
3. The use of concomitant medications, which are known to affect perampanel or the use of any concomitant medications that may alter cognitive function (see Section VIII.F for a partial list).
4. Prior adverse reaction to or prior hypersensitivity to perampanel.
5. Prior participation in studies involving perampanel.
6. Subjects who have received any investigational drug within the previous thirty days.
7. Subjects with IQ \leq 80 as determined by the Peabody Picture Vocabulary Test after enrollment.
8. Positive pregnancy test. Women of childbearing potential will be required to use approved birth control methods during the study.
9. Presence of lifetime history of suicide attempt (including an active attempt, interrupted attempt, or aborted attempt), or has suicidal ideation in the past 6 months as indicated by a positive response ('Yes') to either Question 4 or Question 5 of the C-SSRS at Screening.
10. Invalid results on computerized cognitive tests at screening as indicated by a 'No' on any of the validity indicators generated in the CNS Vital Signs report and low effort on neuropsychological assessments per investigator judgement.

VI. STUDY PROCEDURES

A. Overview: time and events

The study will employ a randomized, double-blind, parallel group design across different titration rates of perampanel in healthy volunteers. The study consists of 8 visits over an 8-week time period. Subjects will be screened and tested at baseline, and then randomly assigned to receive one of four titration schedules, each lasting 6 weeks. (See Appendix A for a complete study timetable).

B. Blinding and Controls

Subjects and study personnel will be blinded to drug randomization since all study drugs will be over-encapsulated in identical capsules.

C. Dosage Regimen

Subjects will be titrated up to 4mg/day PER or receive placebo according to the dosage schedule below:

Event	1	2	3	4	5	6	7	8
Week	Screen	BL ^a	1	2	3	4	5	6
Clinic Visit	X	X			X			X
Placebo			0mg	0mg	0mg	0mg	0mg	0mg
PER ^b -1			2mg	4mg	4mg	4mg	4mg	4mg
PER ^b -2			2mg	2mg	4mg	4mg	4mg	4mg

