Subjects will be screened to assure they meet all of the inclusion criteria and none of the exclusion criteria. All eligible subjects will be required to give informed consent. A complete history, full physical examination, full neurologic examination, vital signs, laboratory screening (including urine pregnancy test for women of childbearing potential), urine drug screen, IQ screen with Peabody Picture Vocabulary Test, full cognitive battery (see below), and lifetime assessment of suicidal ideation/behavior measured by the Columbia-Suicide Severity Rating Scale (C-SSRS) will be obtained.

Visit 2 Baseline/Randomization (Study week 0)

At this visit all subjects who had successfully completed all screening tests and had no significant abnormalities on baseline laboratory, physical exam, neurologic exam, or IQ testing will be randomized to study drug. At this visit, neuropsychological testing will be conducted before the first dose of study drug is administered. Subjects will be randomized and study drug will be dispensed.

Visit 3 Home testing (Study week 1)

At this visit, a partial neuropsychological assessment of cognitive function and behavioral testing will be performed. The assessments at this visit consist of online CNS-Vital Signs computerized cognitive tests and behavioral questionnaires (Profiles of Mood States

(POMS), Adverse Events Profile (AEP), & cognitive/behavioral subsets of QOLIE-89). Partial neuropsychological assessment will be conducted. Telephone contact will be made to check on adverse events and to encourage compliance.

Visit 4 Home testing (Study week 2)

At this visit, a partial neuropsychological assessment of cognitive function and behavioral testing will be performed. The assessments at this visit consist of online CNS-Vital Signs computerized cognitive tests and behavioral questionnaires (Profiles of Mood States (POMS), AEP, & cognitive/behavioral subsets of QOLIE-89). Partial neuropsychological assessment will be conducted. Telephone contact will be made to check on adverse events and to encourage compliance.

Visit 5 Clinic testing (Study week 3)

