Subjects will be instructed to limit alcohol consumption to no more than ½ ounce of absolute alcohol equivalents per day (approximately one 12 oz. beer, or 1 mixed drink) and no more than 3 ounces per week. Regular consumption of caffeine is allowed but will be limited to two cups on test days. Subjects will be instructed not to consume alcohol 12 hours prior to cognitive and behavioral testing, , or take any over-the-counter medications for at least 72 hours prior to cognitive and behavioral testing. All concomitant medications will be recorded on the case report forms. Any concomitant medications and other agents, which are known to affect perampanel or have significant effects on cognition may not be taken during this trial. A partial list of examples include: anticholinergics, anticoagulants, antidepressants, antiepileptics, antipsychotics, anxiolytics, central nervous system depressants, corticosteroids, doxycycline, erythromycin, H2 antagonists, lithium, methylphenidate, narcotics, quinidine, reserpine, theophylline, and centrally active antihistamines.

IX. CLINICAL AND LABORATORY MEASUREMENTS

A. Clinical Efficacy Measurements (Study weeks -1, 0, 1, 2, 3, 4, 5, & 6)

Neuropsychological testing will be completed at screening (visit 1; study week -1), baseline (visits 2; study week 0), and each week of the ASM treatment period (visits 3-8; study weeks 1-6). The neuropsychological test results from the first screening testing (i.e., visit 1 at -1 weeks) will not be included in the analyses. All subjects will have at least 7 hours of sleep on the evening before the day of cognitive testing. (Note. If the subject does not get the required hours of sleep or takes non-approved medication, caffeine, etc., cognitive and behavioral testing will be rescheduled).

For detailed information regarding all of the cognitive tests refer to Section VII.

B. Clinical Safety Measurements

1. Physical Examinations (Study weeks -1, 3, & 6)

A complete physical and neurological examination will be performed during pre-study screening (visit 1; study week -1) and at the completion of the study (visit 8; study week 6) or early study discontinuation. Brief physical and neurological examinations will be performed at visit 5 (study week 3).

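### The Visit 1 neuropsychological scores are left out of the ANCOVA; entering them as a second pre-treatment covariate is a cheap improvement whose gain depends on correlations the documents do not give

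*Combined protocol and SAP*

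**What the plan says.** Section VI.E lists among the Visit 1 procedures "IQ screen with Peabody Picture Vocabulary Test, full cognitive battery (see below". The dosage table in VI.C and Appendix A mark the full neuropsychological battery at both Visit 1 and Visit 2. Footnote l of Appendix A defines that battery identically for every full-battery visit, apart from the vocabulary test given only at screening. Only subjects who have completed the screening tests go on to randomisation (VI.E, Visit 2).

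On the analysis, Section IX.A says: "The neuropsychological test results from the first screening testing (i.e., visit 1 at -1 weeks) will not be included in the analyses". It gives no reason. Section X.B says: "Unless otherwise specified, baseline neuropsychological data will be based on the Visit 2 assessments". The primary model is a 4 (titration rate) by 6 (week) "ANCOVA controlling for scores at Baseline (visit 2"), and the other covariates are named in one sentence: "We will control for differences across groups in age, gender, and personal/family history of psychiatric disorders". Visit 2 is therefore the only test score on the right-hand side of the model.

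Visit 1 does have another use. Exclusion criterion 10 rejects subjects with "Invalid results on computerized cognitive tests at screening".

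**The concern.** Two measurements of the outcome are taken on each subject before randomisation, and one is left out of the model. The obvious reason would be familiarisation: the first sitting is affected by novelty, so change should not be measured from it. That argument concerns the reference point for change. It does not carry over to a covariate, because the intercept absorbs a mean shift between the two sittings and the score can still predict who will do well later. Visit 1 precedes randomisation, so adjusting for it cannot introduce treatment-related bias.

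What is at stake is precision. The plan has about 19 completers per arm and assumes a maximum difference of 0.24 z (X.A). A more precise comparison of arms would help the titration main effect and the comparisons at single weeks, including weeks 3 and 6 in secondary outcome 1.

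**Working it through.** **Inputs.** Four groups of 19 completers, 76 in total (X.A). Full battery at Visits 1 and 2 (VI.C, VI.E, Appendix A). Screening 1 to 3 weeks before baseline (Appendix A, footnote a). The SD of the composite, the between-session correlations and the covariance structure are not given, so correlations from 0.3 to 0.9 are assumed.

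**The plan's own figures.** Enrolment reproduces: 19 × 4 = 76, and 76 + 15 + 12 = 103. The 18 per group for 80% power cannot be rebuilt, because the SD, the within-subject correlation and the primary alpha are not stated. The plan gives no figure for covariate gain.

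**Formula.** Let y be a post-baseline score, b the Visit 2 score and s the Visit 1 score, each with variance 1. With b alone the residual variance is 1 − r_yb². Adding s reduces it by the fraction

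p² = (r_ys − r_yb·r_bs)² / [(1 − r_yb²)(1 − r_bs²)].

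**Case 1: all sessions correlate equally at r.** Here p² = r²/(1+r)². The residual variance goes from 1 − r² to 1 − 2r²/(1+r). For the mean of the six weekly scores, whose variance is m = (1+5r)/6, it goes from m − r² to m − 2r²/(1+r).

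| r | Single week, before → after | Reduction | Reduction, six-week mean |
|---|---|---|---|
| 0.3 | 0.910 → 0.862 | 5.3% | 14.8% |
| 0.5 | 0.750 → 0.667 | 11.1% | 25.0% |
| 0.7 | 0.510 → 0.424 | 17.0% | 33.3% |
| 0.8 | 0.360 → 0.289 | 19.8% | 36.8% |
| 0.9 | 0.190 → 0.147 | 22.4% | 40.0% |

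**Case 2: screening is a weaker predictor, or correlation decays.**

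- Both screening correlations (with baseline and with later scores) 0.1 below r: 0.510 → 0.459, 0.360 → 0.322 and 0.190 → 0.172 at r = 0.7, 0.8 and 0.9, a reduction of 9-11%.
- Only the screening-to-outcome correlation 0.1 below r, with screening-to-baseline left at r. At r = 0.7, p² = (0.6 − 0.49)²/(0.51 × 0.51) = 4.7%. At 0.8 and 0.9 it is 2.8% and 0.3%. This is less favourable because screening stays just as redundant with baseline.
- Both screening correlations 20% lower in proportion (r = 0.5, 0.7, 0.8): 6-8% for a single week, 14-16% for the six-week mean.
- A stable subject component plus serial correlation (three examples): 4-11% for a single week, 10-17% for the mean.
- Pure first-order serial correlation: r_ys = r_yb·r_bs, so the numerator is zero and the gain is 0% at any r.

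**Case 3: group-by-week contrasts.** Take week 1 minus week 6 with equal correlations. Its covariance with either pre-treatment score is r − r = 0, so the gain is 0%.

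**Cost.** For k test-score covariates the expected variance inflation is about 1 + k/(76 − 4 − k − 2). Going from one to two gives (1 + 2/68)/(1 + 1/69) = 1.0294/1.0145 = 1.015, or about 1.5%. Single-visit error degrees of freedom fall from 71 to 70.

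**Scale in power, on an assumed reading.** Suppose the stated 18 per group and 80% refer to a four-group F test at one visit with alpha 0.05. Power at 19 per group is then 82%. It becomes 84.5%, 87% or 91% if residual variance falls by 5%, 10% or 20%.

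**The case against.** The exclusion is clear, pre-specified and consistent between IX.A and X.B. It creates no bias, no contradiction and no type I error problem. The strongest points against a large gain are these.

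- Equal correlation across sessions is doubtful here. Screening can be up to three weeks before baseline, and the composite includes ratings of recent state: POMS covers the past week, and the QOLIE items are moved to a one-week frame where appropriate. If such scores decay over time, screening adds little beyond Visit 2.
- The scenario in X.A has groups apart at maximum effect and equal by week 6, and Study Question 2 is about habituation. Those are group-by-week patterns, where the gain is about nil.
- Weeks 1, 2, 4 and 5 use the partial battery, so a full-battery Visit 1 composite has no exact counterpart in four of the six weeks.
- The model already adjusts for age, gender and psychiatric history, which may take up some of the same variance.

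All four limit the size of the gain, and none shows harm. The partial-battery point applies equally to the Visit 2 covariate.

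A reader might go further and infer a dependable 10-20% cut in variance at no cost. The documents do not support that. They give no correlation, and for a single week under equal correlation that range needs r of about 0.46 to 0.81. The cost is small but not zero: in the 0.3% case above, the 1.5% inflation exceeds the gain. Nor are the Visit 1 results discarded altogether, since they decide eligibility under criterion 10.

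**Conclusion.** The point holds as a cheap improvement. A pre-randomisation score from the same battery, already collected, is left out of the model without a stated reason, and familiarisation would not justify leaving it out as a covariate.

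The size is conditional on the assumed correlations. At a single week, equal correlation gives the upper range and the weaker-screening or decaying patterns give the lower one; nothing in the documents settles which applies. Some gain is likely for the titration main effect and the week-specific comparisons. None should be counted on for habituation contrasts.

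A reader might also infer that the primary analysis is biased or the trial underpowered as a result. Neither follows. The Visit 2 ANCOVA is valid as written, and the stated sample size does not depend on Visit 1.

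**What to change.** Keep Visit 2 as the baseline and the reference for change. Amend IX.A so that the exclusion of Visit 1 scores covers their use as baseline or outcome, not as a covariate. In X.B, pre-specify before unblinding that the Visit 1 composite enters the ANCOVA as a second pre-treatment covariate for the titration main effect and the week-specific comparisons, including weeks 3 and 6. Build it from the same components, and standardise it in the same way, as the Visit 2 covariate used in that comparison. State that no gain is assumed for the group-by-week test, and leave the sample size unchanged.

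If the sponsor prefers to keep Visit 1 out of the primary model, the same model can be pre-specified as a sensitivity analysis, with the reason for the exclusion stated.

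The change takes a sentence in each of two sections. It needs no new data or visits, and the statistical cost is the small one shown in the working.
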